**IMPACT No. 19649 STATISTICAL ANALYSIS PLAN v.2.0 13 JUL 2020**

- The percentage of patients with no need for analgesic treatment of pain in the target joint from the start of Theraflex/Theraflex Advance until the end of study participation⁴;
- The percentage of patients with a complete withdrawal of analgesic treatment of pain in the target joint⁵;
- The percentage of patients with no need for surgical intervention/ at the end of observation⁶;
- The percentage of patients with no need for an emergency visit due to persisting joint pain during the study⁷;
- The percentage of patients who required intra-articular⁸ injections of glucocorticosteroids⁹ during the observation period;
- The percentage of patients who required intra-articular injections of hyaluronic acid¹⁰ during the observation period;
- The percentage of patients who required PRP injection therapy¹¹ during the observation period.

Additional KOOS subscale assessment:

- The percentage of patients with a $\geq 20\%$ reduction in pain intensity at Visits 2, 3 and 4 in the group of patients with knee OA as assessed using the relevant KOOS subscale.
- The percentage of patients with a $\geq 20\%$ improvement in symptoms at Visits 2, 3 and 4 in the group of patients with knee OA as assessed using the relevant KOOS subscale.
- The percentage of patients with a $\geq 20\%$ improvement in functional activity at Visits 2, 3 and 4 as assessed using the relevant KOOS subscale in the group of patients with knee OA.
- The percentage of patients with a $\geq 20\%$ improvement in quality of life at Visits 2, 3 and 4 in the group of patients with knee OA as assessed using the relevant KOOS subscale.
- Changes for each KOOS question presented in a shift table.

Additional HOOS subscale assessment:

- The percentage of patients with a $\geq 20\%$ reduction in pain intensity at Visits 2, 3 and 4 in the group of patients with hip OA as assessed using the relevant HOOS subscale.

⁴ According to the “MEDICAL DATA COLLECTION AT THE END OF OBSERVATION” form.

⁵ According to the “MEDICAL DATA COLLECTION AT THE END OF OBSERVATION” form.

⁶ According to the “MEDICAL DATA COLLECTION AT THE END OF OBSERVATION” form.

⁷ According to the “MEDICAL DATA COLLECTION AT THE END OF OBSERVATION” form.

⁸ Route of administration will be provided in the CM domain, CMROUTE = “OTHER” or “intra-articular”.

⁹ A list of glucocorticosteroids will be determined using the CM domain: incomplete ATC code H02AB

¹⁰ A list of hyaluronic acid agents will be determined using the CM domain: ATC code M09AX

¹¹ As agreed with the Sponsor and with the help of a medical writer, patients who received platelet-rich plasma treatment from the date of enrollment will be specified.

CONFIDENTIAL/PROPRIETARY

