2	
Originally planned to conduct an observational study of the Theraflex product in 80 study centers of Moscow, St. Petersburg and Yaroslavl regions. In connection with the additional administrative barrier on the part of the Moscow Health Care Department, instead of 40 centers planned for opening in the Moscow region, the number of study centers in Moscow has dropped to 20. Thus, the total number of study centers will not exceed 60, which is 75% of the planned number of clinical centers. In proportion with reduced number of study centers, the number of patients in the study is also reduced by 25%, which in numerical terms approximately corresponds to 1100 patients.
 
In order to calculate the indicator of “patients lost to follow-up subjects”, was made a simple analysis of the V2 frequency on the group of the first 10% of subjects included into the study. The analysis was carried out after 3-6 months from the date of patients recruitment, which corresponds to allowable time-window for the second visit. As a result of this analyses, “patients lost to follow-up” index is about 7%, which is significantly lower than initially assumed figure for this indicator (In the Study Risk Register this risk factor was registered as 20% and above). This additionally makes possible to reduce the study population to
	3.0	4-Jul-2018

	
1100 subjects without negative effect on the result of the whole study.
 
Since the analysis of all variables in the study will be carried out using appropriate methods of descriptive statistics, a decrease in the number of patients cannot have a negative impact on the representativeness.
 
Initially It was planned to have interim analysis after all subjects have completed V2. With this amendment the starting point is changing – Interim analysis will be conducted after 50% of subjects (first 550 enrolled) have completed V2 in order to assess the changes after the first course at the half of the study population..
		
--	---	--	--

6. Milestones

Definitions:

- Start of study: FPFV
- Start of data collection: date of first data entry in database
- End of data collection: date of last data entry in database
- End of study: date of clean database
- Observation period: time-window for data collection
- Final report: final report of study results 12 months after clean database

7. Rationale and background

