9.2.7 Visits

The investigator documents an initial visit, follow-up visits and the end of observation/final visit for each patient in the case report form (CRF). Follow-up visits occur during routine practice, the study protocol does not define exact referral dates for those visits. The end of

observation/final visit is to be documented for a period up to 64 weeks after start of the initial treatment.

The observation period for each patient is up to 64 weeks. If patient switches to another Gl and Ch brand the observation of the patient is terminated.

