**IMPACT No. 19649 STATISTICAL ANALYSIS PLAN v.2.0 13 JUL 2020**

- Frequency and shift tables based on the results of the scale assessment [*very dissatisfied, dissatisfied, neither satisfied nor dissatisfied, satisfied, very satisfied*] presented overall and separately for patients with knee and hip osteoarthritis;
- Descriptive statistics for results and changes from Visit 1 (as the Likert scale data are best described by the median, not the mean, 95% CI is additionally provided for the median).
- Use of analgesics for symptomatic treatment of osteoarthritis:
 - Data will be presented on the patient's additional analgesic treatment of pain in the target joint (no/occasionally/regularly, topical agents/systemic agents/combined treatment) at the time of starting the chondroprotector (Theraflex/Theraflex Advance), at the time of study completion, as well as the investigator's assessment of the dynamics of the analgesic treatment of pain in the target joint from the start of the chondroprotector (Theraflex/Theraflex Advance) until the patient's discontinuation from the study (not changed/increased/decreased/pain treatment was discontinued) and time until complete cessation of analgesic treatment (1 month/ 2 months/ 3 months/ 6 months/ 12 months after the start of the chondroprotector), if it was completely discontinued;
 - Tables similar to those described in section 8.5 will be presented by pharmacological subgroup (3rd level) and chemical subgroup (4th level) for various indications [Symptomatic treatment with analgesics for target joint OA/ Other medication for target joint OA related pain/ Other therapy for target joint OA];

Individual subject data will be presented in listings.

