9.3. Exploratory efficacy analysis

In addition to the primary and secondary endpoints specified in the Protocol, this statistical analysis plan provides for an extended analysis. This exploratory analysis will be carried out in the Full Analysis Set (FAS).

List of parameters to be analyzed:

Additional treatment-related analysis:

- The percentage of patients with no progression of arterial hypertension, diabetes mellitus and obesity at the end of observation³

³ According to the “MEDICAL DATA COLLECTION AT THE END OF OBSERVATION” form.
CONFIDENTIAL/PROPRIETARY

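### SAP 9.3 injection percentages take no account of unequal follow-up, so an early leaver with no injection record counts as not requiring one and need is modestly understated

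*SAP*

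**What the plan says.** SAP 9.3 adds a list of treatment-related percentages to the protocol endpoints and fixes the population: "This exploratory analysis will be carried out in the Full Analysis Set (FAS"). It gives no minimum follow-up. SAP 6 admits to that set any patient with one dose and one efficacy or safety datum after the start of observation.

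The items fall into two groups by data source.

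- **Injections.** Steroid and hyaluronic acid use is identified from the CM (concomitant medication) domain by ATC code and route. PRP patients are to be specified with the sponsor and a medical writer (footnote 11), which does not place PRP in the CM domain. The window for all three is the observation period.
- **Form-based items.** Analgesic need is assessed "from the start of Theraflex/Theraflex Advance until the end of study participation". The other two read "The percentage of patients with no need for surgical intervention/ at the end of observation" and "The percentage of patients with no need for an emergency visit due to persisting joint pain during the study". All three come from the end-of-observation form.

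Protocol 9.2.7 sets the length of the window: "The observation period for each patient is up to 64 weeks". It also says: "If patient switches to another Gl and Ch brand the observation of the patient is terminated". Protocol 9.2.7.3 ends observation on a switch to another SYSADOA as well, and Protocol 9.3.3.14 lists lack of efficacy among the reasons for end of observation.

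SAP 7.2 uses available data only. Neither it nor 9.3 gives a censoring rule, a time-to-event method, or a denominator for these percentages. By contrast, the KOOS and HOOS responder items in 9.3 are tied to Visits 2, 3 and 4.

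**The concern.** A crude percentage over a window that closes at each patient's own exit mixes different lengths of exposure. For the injection items the consequence follows directly from the data source. No CM record means not required, whether the patient was watched for 20 weeks or 64. Events after exit are not seen, yet the patient stays in the denominator as a non-event.

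The direction is therefore known: the percentage requiring injections is too low. It is lower still if those who leave (by switching product, or for lack of efficacy) would have needed injections more often than those who stay. A single-arm descriptive study has no comparator in which the same distortion could cancel, and the percentage is itself the reported result.

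**Working it through.** The plan states no figure for these percentages, so there is nothing to reproduce. The size has to be illustrated under assumptions.

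**Inputs**
- Follow-up horizon T = 64 weeks (Protocol 9.2.7).
- True 64-week need p: not in the documents; assumed 10% and 30%.
- Share leaving early e: assumed 7% and 20%. Protocol Amendment 2 gives about 7%, but only for the Visit 2 window in the first 10% of subjects. The same amendment says the risk register had 20% and above.
- Exit times: assumed evenly spread over weeks 2 to 64.
- Hazard: assumed constant. Leavers have r times the stayers' hazard, r = 1 or 3 (assumed).

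**Formulas**
- Stayer hazard h solves (1−e)(1−exp(−64h)) + e(1−exp(−64rh)) = p.
- Mean observed need in leavers: M = 1 − [exp(−2rh) − exp(−64rh)] / (62rh).
- Crude percentage = (1−e)(1−exp(−64h)) + eM.
- Kaplan-Meier limit = 1 − exp(−∫ from 0 to 64 of the average hazard), where the average of h and rh is weighted by stayers and leavers still at risk at each time.
- Completers only = 1 − exp(−64h).

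**One patient.** With p = 30% and r = 1, h = −ln(0.70)/64 = 0.005573. The chance of a need by week 20 is 1 − exp(−20 × 0.005573) = 10.5%, against 30% by week 64. The SAP gives both patients the same weight.

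**Worst scenario shown, p = 30%, e = 20%, r = 3.** h = 0.004213. Stayers' need is 23.63% and leavers' true need 55.46%. Check: 0.8 × 23.63 + 0.2 × 55.46 = 30.0. Observed need in leavers is M = 32.40%. Crude = 0.8 × 23.63 + 0.2 × 32.40 = 25.4%, which is 4.6 points too low.

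**Mildest scenario, p = 10%, e = 7%, r = 1.** M = 5.25%. Crude = 0.93 × 10 + 0.07 × 5.25 = 9.67%, which is 0.33 points too low.

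| True need | Exits | r | Crude | Understated by | Kaplan-Meier | Completers only |
|---|---|---|---|---|---|---|
| 10% | 7% | 1 | 9.67 | 0.33 | 10.00 | 10.00 |
| 10% | 7% | 3 | 9.21 | 0.79 | 9.50 | 8.91 |
| 10% | 20% | 1 | 9.05 | 0.95 | 10.00 | 10.00 |
| 10% | 20% | 3 | 8.09 | 1.91 | 8.85 | 7.37 |
| 30% | 7% | 1 | 29.05 | 0.95 | 30.00 | 30.00 |
| 30% | 7% | 3 | 28.25 | 1.75 | 28.99 | 27.59 |
| 30% | 20% | 1 | 27.28 | 2.72 | 30.00 | 30.00 |
| 30% | 20% | 3 | 25.39 | 4.61 | 27.41 | 23.63 |

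Kaplan-Meier is closer to the truth than the crude figure in every row. It is exact only when exit is unrelated to outcome (r = 1). The completers-only figure is also right when r = 1, but with r = 3 it is further from the truth than the crude figure.

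**The case against.** The best defence is about proportion. The items were added by the SAP as exploratory, the study is descriptive and unpowered (SAP 4.3), and no test or decision hangs on them. Protocol 9.2.7.4 keeps patients under documentation after therapy stops, which limits early exit. SAP 8.1 tabulates numbers at each visit and reasons for withdrawal, so attrition is visible. With 7% exits the error above is only 0.3 to 1.8 points. All of this stands, and it limits the priority. It does not correct the percentages: continued documentation does not cover a switch, withdrawal of consent or loss to follow-up, and a disposition table does not change a numerator or denominator. The 7% is also not a 64-week figure.

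A reader might infer four stronger points that the documents do not support.

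- **That every early leaver counts as a success on the analgesic, surgery and emergency-visit items.** These depend on a completed end-of-observation form. Without one, the available-data rule may remove the patient from the denominator. SAP 9.2 speaks of assessment up to discontinuation, which suggests that leavers also get the form, but this is not settled.
- **That a patient leaving in the first few weeks is the clear example.** The next visit window after Visit 1 is week 16-24, and the start of observation in the FAS definition is not defined, so such a patient may not be in the FAS. An exit at about week 20 avoids this doubt.
- **That early exit flatters "time until complete cessation of analgesic treatment" in SAP 9.2.** Early exit hides later cessations, so it works against the product there, as it does for the percentage with complete analgesic withdrawal.
- **That the SAP presents these as 64-week rates.** It does not label them so; it gives no time anchor at all.

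**Conclusion.** The point holds for the steroid and hyaluronic acid injection items, and for PRP as far as it is handled in the same way. These are crude FAS proportions over unequal follow-up, and they understate need. Under constant hazard, evenly spread exits, true need of 10-30%, exits of 7-20% and leaver hazard of one to three times, the understatement is about 0.3 to 4.6 percentage points. Those rates are assumptions, so the range shows scale and does not predict the result.

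For the form-based items the firm finding is narrower: the denominator and the treatment of early leavers are not stated, and the same bias arises only if early leavers have a completed form.

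This is a cheap improvement to exploratory, descriptive output. Priority is low to moderate.

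**What to change.** - **Injection items with start dates.** Report Kaplan-Meier cumulative incidence to week 64, with follow-up censored at last contact. State the time origin and how partial start dates are handled. Add a sentence that this reduces but does not remove the bias if exit is related to outcome. SAP 8.5 already lists start dates among the medication data collected.
- **PRP.** Confirm first that dates are available. If they are not, give the crude percentage with follow-up time beside it.
- **Analgesic, surgery and emergency-visit items.** State whether early leavers complete the form and what the denominator is. Show three percentages side by side, with follow-up time: all patients with a form, those observed to at least week 56 (the start of the final visit window), and early leavers. Do not make the completers' figure the main result.

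**Cost.** SAP wording and a few more tables, mostly from data already planned. The injection figures will probably look slightly less favourable.

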**IMPACT No. 19649 STATISTICAL ANALYSIS PLAN v.2.0 13 JUL 2020**

- The percentage of patients with a $\geq 20\%$ improvement in symptoms at Visits 2, 3 and 4 in the group of patients with hip OA as assessed using the relevant HOOS subscale.
- The percentage of patients with a $\geq 20\%$ improvement in functional activity at Visits 2, 3 and 4 as assessed using the relevant HOOS subscale in the group of patients with hip OA.
- The percentage of patients with a $\geq 20\%$ improvement in quality of life at Visits 2, 3 and 4 in the group of patients with hip OA as assessed using the relevant HOOS subscale.
- Changes for each HOOS question presented in a shift table.

10. Safety analysis

Safety endpoints:

- Review of drug utilization.
- AEs and SAEs.
- Vital sign measurement results.
- Physical examination results.

10.1. Study drug administration

The following information about Theraflex and Theraflex Advance utilization should be captured in the CRF:

- Start/end of treatment
- Dose/frequency of treatment

For each subject, the following parameters representing the extent of exposure will be calculated:

- Treatment duration.
- Cumulative dose.

Treatment duration (in days) will be calculated using the formula: $[(\text{end date} - \text{start date}) + 1]$.

The resulting cumulative treatment dose will be calculated as the number of capsules taken during the study.

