9.2. Secondary efficacy endpoint analysis

Secondary endpoints:

- Drug utilization of Theraflex® therapy as reported by the patient to their physician:
 - frequency table with assessment of treatment duration will be presented as an assessment of the drug utilization. The results will be presented by the following categories:
 - patients treated with Theraflex® for up to 1 month inclusive: (the assessment will be performed using the collected start and end dates of treatment, this category includes patients falling under the following time period: [0 days < duration for a patient \leq 30.42 days]);
 - patients treated with Theraflex® for 1-3 months: this category includes patients falling under the following time period: [30.42 days < duration for a patient \leq 91.25 days];
 - patients treated with Theraflex® for 3-6 months: this category includes patients falling under the following time period: [91.25 days < duration for a patient \leq 182.50 days];
 - patients treated with Theraflex® for more than 6 months: this category includes patients falling under the following time period: [duration for a patient > 182.50 days];
 - frequency table with the investigator's assessment of compliance with recommendations for duration of treatment with Theraflex/Theraflex Advance (Mostly complied with/Mostly not complied with).
- Patient satisfaction measured with a Likert response scale:

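### Does the SAP's mixed use of Theraflex and Theraflex Advance leave the study drug undefined for the drug-utilization results?

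*SAP*

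**What the plan says.** The SAP uses two labels for the treatment under observation.

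- **Theraflex alone.** This label is used in the objectives and endpoints (section 3), the entry rule of the full analysis set (section 6) and the four duration categories (section 9.2), the first of which reads "patients treated with Theraflex® for up to 1 month inclusive".
- **Both names.** In section 9.2 the investigator's "assessment of compliance with recommendations for duration of treatment with Theraflex/Theraflex Advance" is tabulated, and analgesic use is described "at the time of starting the chondroprotector (Theraflex/Theraflex Advance") and, for its course, "from the start of the chondroprotector (Theraflex/Theraflex Advance"). Section 9.3 has a percentage of patients needing no analgesic "from the start of Theraflex/Theraflex Advance until the end of study participation". Section 10.1 opens: "The following information about Theraflex and Theraflex Advance utilization should be captured in the CRF".

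Exposure in section 10.1 is one duration and one capsule count per subject: "The resulting cumulative treatment dose will be calculated as the number of capsules taken during the study". Sections 9 and 11 give results by diagnosis and overall, not by product.

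In the available text the protocol names Theraflex only: in the inclusion criteria (9.2.2), the satisfaction item (9.3.3.9), the drug-utilization variables (9.3.3.11) and the analysis population (9.7.1).

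**The concern.** Drug utilization is a secondary objective, so what counts as the drug is part of the result. The SAP names Theraflex Advance five times and the available protocol text not at all. No visible sentence says whether the shorter name covers the longer one. Within section 9.2 both labels appear under a single endpoint.

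Three things could be at stake:

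- The duration table in section 9.2 and the exposure duration in section 10.1 could disagree for the same patient.
- A patient who took only Advance could be left out of the full analysis set.
- The first and last dose dates in section 7.2 sort other therapies into prior, concomitant and post-treatment, and the first dose date also identifies treatment-emergent events. Both dates depend on which product counts.

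A reader of the report might also not see that two named products had been pooled.

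**Working it through.** The plan gives no figure to reproduce. The check sets the rules side by side and then asks what each reading would do.

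**1. Where each label appears**

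| Rule | SAP section | Label |
|---|---|---|
| Full analysis set | 6 | Theraflex |
| Duration categories | 9.2 | Theraflex |
| Compliance with recommended duration | 9.2 | both |
| Analgesic use (two mentions) | 9.2 | both |
| Analgesic-free percentage | 9.3 | both |
| Exposure | 10.1 | both |

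Mentions of Theraflex Advance: 1 + 2 + 1 + 1 = 5.

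**2. What the rules say when read together**

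- In section 9.2 the duration table and the compliance table both sit under one heading, the endpoint on utilization of Theraflex. The compliance table names both products, so the heading must cover both.
- Later in section 9.2 the two names stand in parentheses after a singular noun, the chondroprotector. They are treated as one study treatment.
- Section 10.1 deals with administration of the study drug and lists both products there.
- Section 9.2 bases duration on the recorded start and end of treatment. Section 10.1 says that start and end are recorded for both products. The two tables draw on the same dates, and no rule tells the analyst to drop the dates of one product.

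**3. What the strict reading would do**

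The cut-offs in section 9.2 are 30.42, 91.25 and 182.50 days, and the lowest category requires "0 days < duration for a patient". The patients below are invented for illustration.

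| Patient | Theraflex days | Advance days | Theraflex only | Both counted |
|---|---|---|---|---|
| A | 60 | 60 | 60: 1-3 months | 60 + 60 = 120: 3-6 months |
| B | 120 | 90 | 120: 3-6 months | 120 + 90 = 210: more than 6 months |
| C | 0 | 60 | 0: no category | 60: 1-3 months |

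The arithmetic is right, but it does not show a fault in the plan:

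- **Patient C.** If Advance is not Theraflex, this patient fails the inclusion criterion in protocol 9.2.2 and has no dose that meets the entry rule in SAP section 6. Secondary endpoints are analysed in that set, so the patient never reaches the duration table. The missing category is not an anomaly of the cut-offs.
- **Patients A and B.** If Advance counts as another glucosamine and chondroitin brand, protocol 9.1 and 9.2.7 end observation at the switch, so the second period would not be followed. If it is the same brand, both periods count. Neither consistent reading makes the two tables disagree. That happens only if Advance is included in section 10.1 and excluded in section 9.2.

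**4. Possible size**

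The documents do not give the share of patients on Advance. Assumed shares of 1%, 5%, 10% and 20% of the planned 1100 would be 11, 55, 110 and 220 patients. These are the numbers whose classification would depend on the label if the strict reading were used. They do not estimate an error under the reading that the SAP supports.

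**The case for a change.** The strongest case for a change is that in a descriptive study the label on a table is part of the finding. Section 10.1 joins the names with *and*, which suggests that the authors had two products in mind, yet it plans a single capsule count. One defining sentence would cost almost nothing. A table of product at Visit 1, with duration and capsules per product, would show readers what was pooled.

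Part of this stands. The wording is uneven, the available text does not define the term, and one sentence would be a courtesy to the reader. A count of patients by product would be a reasonable optional addition if the CRF recorded it.

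The rest does not carry. No objective or endpoint in either document asks for a comparison or breakdown by product, and the study is unpowered and descriptive. Leaving out that breakdown makes no planned result wrong. The opening pages of the SAP and the first three items of its change list are not in the available text, so a definition may already exist there. For the same reason, the statement in SAP section 13 that there are no departures from the protocol cannot be faulted. The undefined treatment group in the vital-signs table (section 10.5.1) and the differing switch wording in protocol 9.1, 9.2.7 and 9.2.7.3 are separate matters and do not mention Advance.

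**Conclusion.** The inconsistency in naming is real, but no change to the plan is needed. Read together, sections 9.2 and 10.1 lead an analyst to count both products as study drug. The full analysis set, the duration categories and the exposure measures then agree with one another.

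The expected effect on any planned result is nil on that reading. The shifts shown for the invented patients arise only if the analyst applies one definition in section 9.2 and another in section 10.1, which the SAP does not ask for.

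The conclusion rests on two assumptions: that Theraflex serves as the common name for both products, as the structure of section 9.2 indicates, and that treatment dates were recorded for both, as section 10.1 says they should be. The available text neither confirms nor contradicts either one outright. Nothing here says whether the two products have the same effect, and nothing is implied about how any patient should be treated.
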